3.4. Selection of Study Population

The study population consists of patients of both sexes who have a confirmed diagnosis of PI and require immunoglobulin replacement therapy due to hypogammaglobulinaemia or agammaglobulinaemia. All patients are established on a consistent or stable mg/kg dose of any SCIG treatment for a minimum of 3 months prior to Screening (Note: patients entering Cohort 3 must be on weekly SCIG infusions for a minimum of 12 weeks). IgG trough levels of 2 previous SCIG infusions are required within one year of Screening, with 1 trough level obtained within 3 months prior to enrollment. A trough serum IgG level ≥ 5.0 g/L in 2 previous infusions is required. Patients with no prior IgG trough level within 3 months prior to enrollment may use the Screening IgG trough level as their 2nd reading.

Property of Octapharma. Do not copy or distribute without written permission.

4. Sequence of Planned Analyses

4.1. Final Analyses and Reporting

As stated in section 3.3, each patient is treated with *CUTAQUIG* over a total period of approximately 28 weeks; one to two weeks after the last infusion a follow-up visit is performed, and the patient will be switched to a commercially available immunoglobulin product at the discretion of the investigator. Once the last patient has completed the study, data validation will be completed and the database will be locked according to the applicable standard operating procedures. This process includes a data review, the identification and classification of any protocol violations as detailed in section 6, and thus the patient disposition with respect to the analysis populations.

As patients exit the trial, all data will be reviewed and source data verified. Once a patient's data is considered clean within the eCRF, the patient may be soft locked in order to facilitate database lock in the near future.

All final, planned, analyses identified in the protocol and in this SAP will be performed only after the last patient has completed the study, the subject disposition has been agreed and documented, and the final SAP has been approved.

Key statistics and study results will be made available to the study team following database lock and prior to completion of the final CSR by means of tables, figures and listings.

Any, post-hoc, exploratory analyses completed to support planned study analyses, which were not identified in the final SAP, will be documented and reported in appendices to the CSR. Any results from these unplanned analyses will also be clearly identified in the text of the CSR.

5. Sample Size Determination

Approximately 65 patients who meet eligibility criteria will be enrolled in the study:

- At least 15 patients in Cohort 1
- At least 15 patients in Cohort 2
- At least 35 patients in Cohort 3

The co-primary endpoints will be analyzed descriptively, and no formal sample size calculation was done for the overall number of patients enrolled.

For Cohort 3 we plan for a confirmatory analysis to evaluate whether the total IgG trough levels are maintained by an every other week dosing regimen; the following pair of hypotheses will be tested:

$$H_a: T_{eow} > T_w - 1 \text{ vs. } H_0: T_{eow} \leq T_w - 1$$

where T_{eow} is the mean total IgG trough on steady-state dosing every other week, T_w is the same for weekly dosing, and a maximum decrease of 1 g/L for the mean total IgG trough level is considered acceptable.

T_w will be determined after completion of the Stabilization Period, T_{eow} at a given subject's final study visit where a valid IgG trough level is collected and reported within a suitable visit window. If a subject terminates from the study prior to the end of study visit (2 weeks following Week 24 infusion), or if a completed subject's end of study IgG trough is not valid or not collected, then the last study visit where a valid IgG trough level was collected will be considered T_{eow} .

This one-sided hypothesis will be tested by a paired t-test at the alpha=2.5% level of significance. Assuming 3.0 for the standard deviation common to both members of a pair, and 0.8 as the correlation between members of a pair, this results in a required minimum of 31 evaluable patients to achieve a power of 80%.

5.1. Patient Replacement Policy

Patients withdrawn from the study for any reason will not be replaced.

5.2. Premature Termination of the Study

Both, the responsible Investigators and the Sponsor, reserve the right to terminate the study as a whole or center-wise at any time. Should this be necessary, the procedures will be arranged on an individual study basis after review and consultation by both parties. In terminating the study, the Sponsor and the Investigator will ensure that adequate consideration is given to the protection of the patients' interests. Premature termination will be notified in accordance with applicable regulatory requirements. Please refer to the protocol for further details on premature termination.

At any time, the study as a whole will be terminated prematurely if:

- New toxicological or pharmacological findings or safety reports invalidate the earlier positive benefit-risk assessment.
- If more than independent 2 TEEs (ie, ischemic stroke, transient ischemic attack, cerebral infarction, cerebrovascular accident, cerebral thrombosis, embolic infarctions, [acute] myocardial infarction, deep vein thrombosis, pulmonary embolism, venous thrombosis excluding thrombophlebitis) are observed fulfilling the following criteria:
 - Assessed as probably or possibly related to CUTAQUIG treatment by Investigator and/or Sponsor
 - Confirmed by the IDMC

- Any other reason rendering the continuation of the study impossible for the Sponsor

At any time, the study can be terminated at an individual study site if:

- The site cannot comply with the requirements of the protocol
- The site cannot comply with applicable standards
- The site does not meet the required recruitment rate

Should the study be prematurely terminated, all study materials, including IMP, must be returned to the Sponsor.

Property of Octapharma. Do not copy or distribute without written permission.

6. Analysis Populations

The following populations will be considered for the statistical analysis:

The safety analysis set (SAF) consists of all patients who received at least part of one infusion of CUTAQUIG.

The full analysis set (FAS) is defined as all patients in the Safety Analysis Set who satisfy all major eligibility criteria and for whom any post-baseline data is available (per intention-to-treat principle). This set of eligible patients will be used for measurement of treatment effects. It is expected that the FAS will coincide with the safety set.

The per-protocol (PP) set consists of all patients in the FAS, excluding those with substantial protocol deviations which may have an impact on the analysis of the co primary endpoints. This is the set of patients who participated in the study as intended and for whom the co primary endpoints can be evaluated as planned.

Only protocol deviations with the potential to significantly affect the study results or to invalidate the interpretation of the data obtained will lead to exclusion of patients from the PP set.

Efficacy endpoints will be analyzed using the FAS. Safety endpoints will be analyzed using the Safety Analysis Set. Selected analyses will be repeated for the PP population as detailed in the SAP and its appendices.

In the event that a patient is not treated according to the dosing regimen described for his assigned cohort, the original cohort assignment will still be used for safety and the ITT analyses (SAF and FAS populations). These patients will be removed from the PP population due to protocol violations.

The membership of each patient in the respective analysis populations will be determined before statistical analysis in a data review meeting by a panel consisting of a medical expert from the Sponsor, the clinical study manager, the data manager and the study statistician. Protocol deviations to be considered will include (but not limited to):

- Violations of the study entry criteria.
- Administration of any other blood or plasma-derived product or of any other immunoglobulin preparations during the SCGAM-06 study.
- Any prohibited concomitant medication.
- Failure to attend two scheduled consecutive visits OR three or more scheduled visits during the study for reasons other than clinical reasons.

Any analysis might be repeated on basis of the PP analysis set if indicated by the data or in case the PP population differs from the FAS by 3 patients or more, to allow for an assessment of the robustness of the results with respect to protocol violations.

All protocol violations documented during the conduct of the study or identified at the data review process prior to DB lock will be reviewed and classified as substantial or non-substantial and with respect to its effect on the planned analysis. Only substantial protocol violations with the potential to significantly affect the study results or to invalidate the interpretation of the data obtained will lead to exclusion of patients from the PP set.

7. General Issues for Statistical Analysis

Descriptive summaries will be presented for each of the primary and secondary variables. In general, summaries will be completed for all patients overall and by study cohort if applicable.

Continuous, quantitative variable summaries will in general include the number of patients with non-missing values (N), mean, standard deviation, median, minimum and maximum, 1st and 3rd quartile.

Categorical, qualitative variable summaries will include the frequency and percentage of patients who are in the particular category. In general the denominator for the percentage calculation will be based upon the total number of patients in the analysis population unless otherwise specified.

7.1. Analysis Software

Statistical analyses will be performed using SAS Software version 9.3 or higher. Also, PRO CoRE 2.1 Smart Measurement® System software will be used to derive the component scores for the SF-36 and SF-10 questionnaires.

7.2. Withdrawals

Patients who withdraw from the study prematurely will be considered in all data presentations for which they contribute data; in particular for the analysis of annual rates they will be considered with their actual observation periods.

7.3. Handling of Missing Data

In general, missing data will not be imputed: calculations pertaining to person-year computations will be based on observed values only.

For missing weight measurements the last available body weight will be used for all calculations related to dosing; in individual patient data listings missing data will however not be replaced by imputed values.

No analyses of the patterns of missing data will be done.

For adverse events the following will be applied:

An Adverse Event (AE) is defined as treatment-emergent, if first onset or worsening is after start of the first infusion of *CUTAQUIG*.

If the start date and time of an AE are partially or completely missing, the AE will be assumed to be treatment-emergent if it cannot be definitely shown that the AE did not occur or worsen during the treatment emergent period (worst case approach). Missing dates and times will not be replaced.

For medications the following will be applied: A medication will be considered prior if it starts before and ends before the day of first dose of study drug. A medication will be considered concomitant if it is taken on or after the day of first dose of study drug. A medication will be assumed to be concomitant if it cannot be definitely shown that the medication was not administered on or after the first dose of study drug. Missing dates will not be replaced.

7.4. Derived and Computed Variables

The following derived and computed variables have been initially identified as important for the analysis of the primary and secondary target variables. It is expected that additional variables will be required. The SAP will not be amended for additional variables that are not related to the primary target or key secondary target variables. Any additional derived or computed variables will be 090-SAP-SCGAM-06-clean version3.0_13FEB2022

identified and documented in the SAS programs that create the analysis files. If the SAP is not amended, further derivations related to primary and secondary target variables will be described in the CSR.

- **Age** will be derived according to the usual definition that a person is n years old until she or he has completed her or his $(n+1)^{\text{th}}$ year of life, using the date of informed consent as the reference date. This is also the definition that will be applied for evaluation of the age related inclusion criteria [Unit: years]
- **Body Mass Index:** $\text{BMI} = (\text{Body weight}) / \text{Height}^2$ [Unit: kg/m^2]
- The **CUTAQUIG stabilization period** is defined for patients that did not participate in the SCGAM-03 trial as the period between the day of first treatment with study drug to the end of the observation period. This will usually be the treatment period baseline visit.
- The **CUTAQUIG treatment period** is defined as the period between the day of first treatment with study drug in a modified dosing regimen to the end of the observation period. For patients that previously completed the SCGAM-03 trial, this is also the period of first treatment with the SCGAM-06 study drug. The end of the observation period will usually be the termination visit.
- The **rate of serious bacterial infections** per year during regularly repeated treatment with CUTAQUIG will be calculated as $r = (\text{Total number of serious bacterial infections occurring in the stabilization and treatment periods}) / (\text{Sum of stabilization and treatment periods})$ [Unit: 1/years]
- The **rate of other infections** will be derived using the same method

Calculation of the confidence intervals of these rates will account for intra-patient correlation in incidents following a compound Poisson process model.[1]

With C_i infections for the i^{th} patient, and C total infections, the adjusted 2-sided 98% CI is calculated by:

$$\left[e^{\ln(r) - 2.33 \cdot \sqrt{\frac{\sum C_i^2}{C^2}}} ; e^{\ln(r) + 2.33 \cdot \sqrt{\frac{\sum C_i^2}{C^2}}} \right]$$

If there are 0 infections, an alternative method will be used to approximate the upper bound on the 98% confidence interval using a chi-square distribution and the following SAS code:

```
data poisson;
events=0;
sumyrs=xxx;
ul=cinv(0.99,2*(events+1))/2;
rate=events/sumyrs;
ulinc=ul/sumyrs;
run;
where
sumyrs = duration of treatment in years
events = total number of events
```

rate = total number of events per person-year

ulinc = two-sided 98% CI - upper limit

- The **rate of infusions with one or more temporally associated AEs** will be calculated for each patient as $r = (\text{Number of infusions with one or more temporally associated AEs}) / (\text{Number of infusions started})$. An AE is defined as a temporally associated if, and only if, the onset (or worsening) is either during an infusion of study medication or within 72 hours of the end of the infusion. [Unit: N/A]

Property of Octapharma. Do not copy or distribute without written permission.

8. Study Subjects and Demographics

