Patients entering the study currently active and established on CUTAQUIG in Study SCGAM-03 will have the Treatment Period Baseline Visit performed on the same day as Termination Visit on Study SCGAM-03. Patients must first complete their termination procedures for SCGAM-03, prior to their first infusion for Study SCGAM-06. Procedures that are performed on the same day as part of Study SCGAM-03 termination that are also required as part of Study SCGAM-06 Baseline, do not need to be repeated. Patients who completed the SCGAM-03 study and went on a commercial SCIG product prior to screening for SCGAM-06 are required to complete the Stabilization Period.

Number of Patients:

Approximately 65 patients are planned for this study.

- At least 15 patients in Cohort 1
- At least 15 patients in Cohort 2
- At least 35 patients in Cohort 3

Patient Selection Criteria:

Inclusion Criteria:

1. Age \geq 2 years and \leq 75 years.
2. Confirmed diagnosis of primary immunodeficiency (PI) disease as defined by the European Society for Immunodeficiencies and Pan American Group for

Name of Sponsor/Company: Octapharma USA, [name]	
Name of Investigational Product: CUTAQUIG	Protocol Identification Code: SCGAM-06
Name of Active Ingredient: Human Normal Immunoglobulin	Date of Final Protocol: 28-Aug-2019

Immunodeficiency and requiring immunoglobulin replacement therapy due to hypogammaglobulinaemia or agammaglobulinaemia. **Note:** The exact type of PI disease will be recorded.

3. Established on a consistent or stable mg/kg dose of any SCIG treatment for a minimum of 3 months prior to Screening. **Note:** patients entering Cohort 3 must be on weekly SCIG infusions for a minimum of 12 weeks.
4. Availability of the Immunoglobulin G (IgG) trough levels of 2 previous SCIG infusions within 1 year of Screening, with 1 trough level obtained within 3 months prior to enrollment, and maintenance of trough serum IgG levels ≥ 5.0 g/L in 2 previous infusions. Patients with no prior IgG trough level within 3 months prior to enrollment may use the Screening IgG trough level as their 2nd reading.
5. Voluntarily given, fully informed signed informed consent. For patients under the legal age of consent, voluntarily given, fully-informed, signed informed consent will be provided by patient's parent or legal guardian, and assent will be provided by patient (per age-appropriate Institutional Review Board [IRB] requirements).

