After completing the Screening Period during which they will be assigned to 1 of the 3 study cohorts, patients will enter a 4-week Stabilization Period. During the Stabilization Period, patients will receive CUTAQUIG infusions at the same body-weight dependent dose and infusion rate as their previous SCIG product prior to entering the Treatment Period; however, this flow rate should not exceed maximum infusion rates listed in protocol (Section 5.5.3). Patients will receive 4 CUTAQUIG infusions during the Stabilization Period. Patients entering the study currently active and established on CUTAQUIG in Study SCGAM-03 will have already been stabilized on CUTAQUIG and will go directly into the Treatment Period following the Screening Visit. Patients that completed the SCGAM-03 study and went on a commercial SCIG product prior to entering SCGAM-06 are required to enter the Stabilization Period. During the Treatment Period, patients will receive CUTAQUIG infusions according to their assigned-cohort infusion parameters.

Throughout the study, the following interventions and procedures will be performed at predefined time points (Section 6.1.2 and the Flow Charts of Assessments Table 1 [Screening and Stabilization Periods], Table 2 [Cohort 1], and Table 3 [Cohort 2], Table 4 [Cohort 3]): blood draws for laboratory assessments, body weight measurement, patient diary review, physical examination including vital signs, local infusion-site reaction assessments, urine sampling, urine pregnancy tests, QoL assessments, and the Subject Questionnaire. AEs and any changes in concomitant medications will be recorded throughout the study period.

Patients who enter and participate in one cohort may not enter another cohort at a later time.

An Independent Data Monitoring Committee (IDMC) will periodically review relevant data throughout the study with emphasis on adverse events including serious adverse events and thromboembolic events.

The study will be conducted at study sites in the USA.

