6.2 Duration of Study

6.2.1 Planned Duration for an Individual Patient

The duration for each patient in the study will be approximately 30 to 32 weeks: approximately 1 to 2 weeks in the Screening Period, 4 weeks in the Stabilization Period, 24 weeks in the Treatment Period, and 1 to 2 weeks to Termination Visit.

Patients entering the study established on weekly SCIG infusions will have a 1 week Screening Period. Patients entering the study established on every other week dosing will have a 2 week Screening Period.

Patients entering the study currently active and established on SCGAM-03 CUTIQUIG will skip the 4 week Stabilization Period.

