3.3. Overall Study Design and Plan

Study SCGAM-06 is designed as a prospective, open-label, non-controlled, 3-arm, multicenter, phase 3 study with observation of patients receiving weekly doses of CUTAQUIG at increasing infusion volumes or flow rates, receiving every other week doses of CUTAQUIG at double the weekly dose, over a period of up to approximately 6 months.

The study will be conducted at approximately 15 study sites in the United States of America.

Patients who participated in the SCGAM-03 trial may be provided the opportunity to participate along with new patients.

After completing the Screening Period and being assigned to 1 of 3 cohorts (as described below), patients will enter a 4-week Stabilization Period that will allow one to adjust and familiarize to CUTAQUIG. Patients completing the SCGAM-03 study at the same time of screening for the SCGAM-06 study will not be required to go into the Stabilization Period. Following the Stabilization Period, patients will enter a 24 week Treatment Period and begin their infusion parameters according to their Cohort assignments:

Cohort 1 (increased volume at each infusion site – patients will receive CUTAQUIG weekly and increase infusion volumes every 4 weeks): Patients will return to the clinic for the Treatment Period Baseline Visit, at which they will receive the same body-weight dependent (mg/kg) dose but the volume per site will be increased by up to 25 mL/site for patients ≥ 40 kg or 10 mL/site for patients < 40 kg. Patients will receive this new volume per site for 4 weekly infusions (Treatment Period Baseline and Weeks 1, 2, and 3), and return to the clinic at Week 4 for their next infusion at an increased volume at each infusion site. This cycle will continue, with infusion volumes increasing up to 25 mL/site for patients ≥ 40 kg or 10 mL/site for patients < 40 kg every 4th infusion until reaching a patient's maximum dose (in mL), maximum tolerated volume (maximum volume based on Investigator's decision of patient's tolerance), or 100 mL at 1 injection site – whichever is lower.

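### SAP 7.4 gives no stabilization period to SCGAM-03 completers who must stabilize, so their first four infusions fall in the wrong period or in none

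*SAP*

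**What the plan says.** SAP 7.4 lists derived variables that it regards as important for the primary and secondary target variables. Two of them are study periods.

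- Stabilization period: it "is defined for patients that did not participate in the SCGAM-03 trial" and usually ends at the Treatment Period Baseline visit.
- Treatment period, first sentence: it "is defined as the period between the day of first treatment with study drug in a modified dosing regimen" and usually ends at the termination visit.
- Treatment period, second sentence: "For patients that previously completed the SCGAM-03 trial, this is also the period of first treatment with the SCGAM-06 study drug".

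Protocol 3.2 sets a different rule on who stabilizes: "Patients that completed the SCGAM-03 study and went on a commercial SCIG product prior to entering SCGAM-06 are required to enter the Stabilization Period". The Study Outline repeats it for patients who "went on a commercial SCIG product prior to screening for SCGAM-06 are required to complete the Stabilization Period", and so do the footnotes to Table 1, the glossary and Protocol 6.1.2. The exemption is only for patients still active in SCGAM-03 at screening. SAP 3.3 has the same exemption: "Patients completing the SCGAM-03 study at the same time of screening for the SCGAM-06 study will not be required to go into the Stabilization Period".

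**The concern.** Temporally associated TEAEs in the Stabilization Period and in the Treatment Period are two separate co-primary variables (Protocol 3.1.1, SAP 3.2.1), each with its own tables in SAP 10.1. SAP 9 also reports infections separately for stabilization and treatment. During stabilization, patients keep their previous dose and flow rate; the modified regimen starts only at the Treatment Period Baseline visit. The split by period therefore separates CUTAQUIG at familiar settings from CUTAQUIG at the settings under study. If the analysis definition puts some patients' stabilization infusions on the wrong side of that line, or on neither side, the by-period results no longer describe what their titles say.

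**Working it through.** The documents state no figure for this point, so the check sets the texts side by side and then counts what is exposed.

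**Step 1. Apply SAP 7.4 to each entry route.**

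- Never in SCGAM-03: the stabilization period is defined, and treatment starts with the first modified-regimen infusion. This is consistent.
- Direct entry from SCGAM-03: there is no stabilization. The first SCGAM-06 infusion is also the first modified-regimen infusion, so both treatment-period sentences give the same start.
- SCGAM-03 completer who used a commercial product in between: the protocol requires stabilization, but SAP 7.4 defines none because the patient took part in SCGAM-03. The first SCGAM-06 infusion is at Stabilization Week 0 and the first modified-regimen infusion is four weeks later. The two treatment-period sentences now disagree.

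For the third group there are two readings:

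- Reading A (SCGAM-03 sentence): the treatment period starts at Stabilization Week 0, and the stabilization infusions count as Treatment Period.
- Reading B (modified-regimen sentence): the treatment period starts at Treatment Period Baseline, and the stabilization infusions are in neither period.

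**Step 2. Infusions per affected patient.** Protocol 3.2: "Patients will receive 4 CUTAQUIG infusions during the Stabilization Period". Protocol 6.2.1 gives "24 weeks in the Treatment Period", and Tables 2 to 4 schedule infusions at both Baseline and Week 24.

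- Cohorts 1 and 2, weekly: 24 + 1 = 25 treatment infusions; 4/(4 + 25) = 4/29 = 13.8%.
- Cohort 3, every other week: 24/2 + 1 = 13 treatment infusions; 4/(4 + 13) = 4/17 = 23.5%.

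**Step 3. Cohort-level share under Reading A.** The number of affected patients, k, is not given. I assume k = 1, 5 or 10 in a cohort of the minimum size N, with all planned infusions given. With m treatment infusions per patient, the share of nominal Treatment Period infusions that are really stabilization is 4k/(mN + 4k).

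- N = 15, m = 25: 4/379 = 1.1%; 20/395 = 5.1%; 40/415 = 9.6%.
- N = 35, m = 13: 4/459 = 0.9%; 20/475 = 4.2%; 40/495 = 8.1%.

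With k = 0 the share is zero. These are shares of infusions, not changes in any reported result.

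**Step 4. Person-time lost under Reading B.** Each affected patient loses 4/52 = 0.077 person-years. If all 65 patients are treated for about 28 weeks (SAP 4.1), the total is 65 × 28/52 = 35 person-years. For k = 1, 5 and 10 in the whole study, the loss is 0.077/35 = 0.2%, 0.385/35 = 1.1% and 0.769/35 = 2.2%.

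**Step 5. Which outputs move.**

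- By-period temporally associated TEAEs: under Reading A, Treatment Period incidence can be too high and Stabilization Period incidence too low. Under Reading B, events linked to the four infusions drop out of both.
- By-period infection rates: events and person-time go to the wrong period under A and are lost under B.
- Pooled SBI rate: SAP 7.4 sums both periods, so A leaves it unchanged. B removes 0.077 person-years per affected patient, and any SBI in that time.
- Overall TEAE counts: unchanged, because treatment-emergence runs from the first CUTAQUIG infusion.

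**The case against.** The strongest reply is that the right rule can be found elsewhere. SAP 3.3 and the protocol glossary agree on who stabilizes, SAP 1 points readers to the protocol, and the safety outputs are descriptive. A careful programmer could resolve the conflict correctly. That is fair, and it limits the seriousness. It does not remove the problem, because SAP 7.4 is where the analysis periods are defined, and neither of its readings gives what the protocol describes.

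A reader might also infer three stronger things that the documents do not support.

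- *That these infusions are certain to be counted as Treatment Period.* The SCGAM-03 sentence says so, but the modified-regimen sentence excludes them. The assignment is unsettled.
- *That the modified-regimen AE rate is diluted.* The by-period outputs in SAP 10.1 are numbers of patients with an event, and SAP 7 takes the analysis population as the general denominator. The Study Outline adds counts of TEAEs by period. Extra infusions can raise these figures or leave them unchanged, but cannot lower them. The per-infusion AE rate in SAP 7.4 and 10.2 has no stated split by period. Only the by-period infection rates have a person-time denominator that could be diluted.
- *That the weekly trough for the Cohort 3 test becomes undefined.* These patients do complete stabilization, and Table 4 schedules a pre-infusion trough at Treatment Period Baseline. The test uses that sample, not the period definition in SAP 7.4.

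**Conclusion.** Wrong as written. SAP 7.4 contradicts the protocol and SAP 3.3 on who has a stabilization period, and its treatment-period definition contradicts itself for SCGAM-03 completers who must stabilize. For each such patient, four infusions are misplaced or unplaced, and any TEAE or infection tied to them is assigned wrongly in the co-primary by-period TEAE tables and the by-period infection rates.

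The effect on results cannot be fixed from the documents. It depends on how many such patients enrolled, which may be none, and on whether they had events in those four weeks. The infusion counts assume the full planned schedule. The Cohort 3 trough comparison and the overall TEAE counts do not depend on this point.

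**What to change.** In SAP 7.4:

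1. Define the stabilization period for every patient with a Stabilization Week 0 infusion, from that infusion until just before the Treatment Period Baseline infusion.
2. Start the treatment period at the Treatment Period Baseline infusion for all patients.
3. Limit the SCGAM-03 sentence to patients who enter directly from that study.

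The misassigned share is then zero whatever the number of affected patients, and SAP 7.4 agrees with SAP 3.3 and the protocol. The cost is a rewording of the two definitions. No new data are needed, because both infusions are given at scheduled on-site visits.
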